### **Labelling**

All study drug supplied by Pfizer will be re-packaged and labelled according to Annex 13 of the 'Good Manufacturing Practice'. The drugs will be re-packaged, labelled, QP released and distributed by Tayside Pharmaceuticals to sites.

## **4.7. Drug Storage Accountability**

### **Storage**

Axitinib should be stored in the original package in order to protect from moisture and should be stored at controlled room temperature (between 15°C and 30°C). The local pharmacy is responsible for ensuring that the study medication is stored in an appropriate secured area. Study treatment must be kept out of the reach and sight of children.

### **Accountability**

The investigator or a delegated individual (e.g. pharmacist) must ensure that the study drug is stored and dispensed in accordance with hospital standard operating procedures and applicable regulatory requirements.

The medication provided for this study is for clinical trial use only as directed. Drug distribution and accountability logs will be provided to the site in a pharmacy pack. It is the investigator's responsibility to establish a system for handling the investigational product to ensure that:

- Deliveries of investigational products from Pfizer via Tayside Pharmaceuticals are correctly received by a responsible person (e.g. pharmacist or suitable pharmacy designee) and are handled and stored correctly and safely.
- Investigational products are dispensed only to study participants, and in accordance with the protocol.
- Participants return any unused investigational product and all empty packs to the investigator.
- A dispensing record (which will include the identification of the participant to whom the investigational product was dispensed, the date of dispensing, the quantity of investigational product dispensed, and the date and quantity of any unused investigational product returned to the pharmacy) is accurately maintained. Any discrepancies must be accounted for on the appropriate form.

In the case that any study drug is damaged, please contact SCTRUM for reconciliation and replacement.

At the termination of the study or at the request of the sponsor, all unused drugs will be accounted for and destroyed locally at the study sites. Certificates of delivery and destruction or return must be signed and copies retained in the Investigator Site File.

Accountability records must be completed and any study drug remaining at the end of the trial must be destroyed according to the sites local standard procedures.

## 5. ASSESSMENT OF EFFICACY

### 5.1. Treatment and Examination Schedule

Activity	Screening (Up to 4 weeks prior to enrolment)	Pre-treatment Day 1, Week 1	Week 3	Week 5	Week 7	Week 9	Week 9 (min 36 hours after stopping axitinib)	6 week post surgery follow up	12 week post surgery follow up
Confirmation of histological diagnosis of ccRCC via image guided biopsy (5 cores: 1 for diagnosis and 4 cores for research as per appendix 6)	X								
Medical History	X								
Physical examination including ECOG & Karnofsky performance status, body weight, height, temperature, blood pressure  , heart rate, respiratory rate.	X	X 	X	X	X	X		X	X
Haematology, coagulation, glucose, renal and liver function, serum calcium, CRP and LDH.	X	X 	X	X	X	X		X	X
Urinalysis for protein	X	X 	X	X	X	X			
Serum Thyroid Function Tests (Free T4 and TSH)	X	X 	X	X	X				
Pregnancy Test (serum or urine) if applicable	X								
CT Chest, Abdomen and Pelvis for IVC VTT and primary tumour assessment using RECIST 1.1 and Mayo classification	X (all)					X (M1 only)			X (all)
CT Chest to check for development of metastasis			X (M0 only)			X (M0 only)			
Contrast enhanced MRI abdomen	X		X			X			
Blood samples and urine sample for biomarker analysis			X	X	X	X			X
Assessment of compliance with study medication				X	X	X			
Dispense axitinib			X	X	X	X			
Dose Escalation (5 to 7 to 10mg BID) (depending on toxicities and blood pressure) 				X	X	X			
Stop axitinib (minimum 36 hours, maximum 7 days prior to surgery)						X			
Assessment of concomitant medications			X	X	X	X			
Assessment of symptoms (CTCAE V4)	X	X	X	X	X	X		X	X
Nephrectomy and IVC tumour thrombectomy							X		

 Laboratory and clinical assessments day 1 week 1 may be omitted if conducted within previous 7 days as part of screening assessment (apart from blood and urine for biomarker analysis).

 Blood pressure readings are required at each time point and should be taken by a healthcare professional using an appropriate calibrated machine.

 Aggressive increasing of axitinib dose at each to ensure effective dose reached in window period.

## 5.2. Schedule of Assessments

### 5.2.1. Screening Procedures

Screening procedures within 4 weeks prior to study enrolment.

- Clinical assessment
  - Signed informed consent
  - Medical history
  - ECOG & Karnofsky performance status (appendix 1)
  - Body weight
  - Height
  - Blood pressure
  - Heart rate
  - Respiratory rate
  - Temperature
  - Symptom assessment (CTCAE V4)
- Histological assessment
  - Confirmation of diagnosis of ccRCC via image guided biopsy (5 cores should be taken for diagnosis/research as per the 'translational research studies' in appendix 6)
- Laboratory determinations
  - FBC, coagulation, glucose, renal and liver function, serum calcium, C - reactive protein (CRP) and Lactate Dehydrogenase (LDH).
  - Urinalysis
  - Serum thyroid function tests (Free T4 and Thyroid stimulating hormone (TSH)).
  - Pregnancy Test (serum or urine) if applicable (must be performed a maximum of 14 days prior to receiving 1st dose of axitinib)
- Radiological assessment
  - CT thorax, abdomen and pelvis for IVC VTT and primary tumour assessment using RECIST 1.1 criteria and the Mayo classification
  - Diffusion/ contrast enhanced MRI abdomen

### 5.2.2. Study Enrolment

The participant's research nurse and/or doctor will screen the participant to ensure that they meet the trial eligibility criteria, after obtaining participant consent for any additional trial procedures.

Patients will be enrolled centrally with the Scottish Clinical Trials Research Unit (SCTRU). An eligibility and enrolment checklist must be completed prior to enrolment. Enrolment should take place within 72 hours prior to the planned start date of axitinib.

Once consent has been obtained and eligibility confirmed the participant should be enrolled by emailing the NAXIVA team at the Scottish Clinical Trials Research Unit:

**SCTRU enrolment email: [[contact]](mailto:[contact])**

Referring to the NAXIVA site instructions, the following information will be required at enrolment;

- Name of hospital, consultant and person enrolling the patient
- Confirmation that the patient has given written informed consent for trial participation and the provision of biological samples.
- Confirmation that the patient is eligible for the trial by completion of the eligibility checklist.
- Patients initials, date of birth, sex, NHS/CHI number and date of proven clear cell RCC (metastatic/ non-metastatic).
- Proposed start date of axitinib (must be within 72 hours of enrolment).

The site will inform the participants General Practitioner (GP) of the participants enrolment, if the participant gives consent to do so.

It may be possible for participants to be recruited into other clinical trials, but this should be discussed with the CI via SCTRUM before this is considered.

### **5.2.3. Pre-treatment Assessment day 1, week 1 (within 7 days)**

- Laboratory determinations\*
  - FBC, coagulation, glucose, renal and liver function, serum calcium, CRP and LDH
  - Urinalysis
  - Serum thyroid function tests (Free T4 and TSH)
  - Blood and urine samples for biomarker analysis (NB. patients should be asked to fast for 6 hours prior to urine analysis, and to not take axitinib until after their bloods have been sampled for the biomarker analyses)
- Clinical assessment\*
  - ECOG & Karnofsky performance status (appendix 1)
  - Body weight
  - Height
  - Blood pressure
  - Heart rate
  - Respiratory rate
  - Temperature
  - Symptom assessment (CTCAE V4)
  - Assessment for concomitant medications.

\*Laboratory and clinical assessments day 1 week 1 may be omitted if conducted within previous 7 days as part of screening assessment (apart from blood and urine for biomarker analysis).

- Radiological assessment
  - CT thorax, abdomen and pelvis for IVC VTT (all patients) and primary tumour assessment using RECIST 1.1 criteria and the Mayo classification (is not required if CT carried out at screening/diagnosis)  
Imaging to be acquired following intravenous contrast medium assuming no contraindications. Thin slice (at least 2mm) imaging will be acquired as an arterial phase in the thorax and as a portal venous phase of the abdomen and pelvis.

- Diffusion/ contrast enhanced MRI abdomen (all patients), (is not required if contrast enhanced MRI carried out at screening/diagnosis)  
Thin slice (or volumetric imaging) will be acquired of the kidneys and adjacent IVC to include the tumour thrombus and proximal normal IVC to allow reconstruction of the VTT in axial and coronal planes. Sequences may include:
  - T2-weighted imaging
  - T1-weighted imaging with and without fat saturationFollowing intravenous contrast injection of a suitable gadolinium-based contrast agent as a dynamic acquisition
  - Diffusion weighted imaging
  - Non-contrast MR venography of the renal veins and IVC including the tumour thrombus and normal venous lumen adjacent to the thrombus
  - The patient may be asked to undergo breathing strategies to enhance imaging (eg. breathhold, valsalva).

- Pharmacy
  - Dispense axitinib

#### **5.2.4. Assessment at day 1, week 3 (within 7 days)**

- Laboratory determinations
  - FBC, coagulation, glucose, renal and liver function, serum calcium, CRP and LDH
  - Urinalysis
  - Serum thyroid function tests (Free T4 and TSH)
  - Blood and urine sample for biomarker analysis (NB. patients should be asked to fast for 6 hours prior to urine analysis)
- Clinical assessment
  - ECOG & Karnofsky performance status (appendix 1)
  - Body weight
  - Height
  - Blood pressure
  - Heart rate
  - Respiratory rate
  - Temperature
  - Symptom assessment (CTCAE V4)
  - Assessment for concomitant medications
  - Assessment of compliance with study medication
  - Dose evaluation and escalation (where appropriate)
- Radiological assessment
  - CT chest for IVC VTT (M0 patients only) to check for development of metastasis
  - Diffusion/ contrast enhanced MRI abdomen (all patients)
- Pharmacy
  - Dispense axitinib (dose modification as per section 4.2 if applicable)

#### **5.2.5. Assessment at day 1, week 5 (within 7 days)**

- Laboratory determinations
  - FBC, coagulation, glucose, renal and liver function, serum calcium, CRP and LDH
  - Urinalysis
  - Serum thyroid function tests (Free T4 and TSH)
  - Blood, urine sample for biomarker analysis (NB. patients should be asked to fast for 6 hours prior to urine analysis)
- Clinical assessment
  - ECOG & Karnofsky performance status (appendix 1)
  - Body weight
  - Height
  - Blood pressure
  - Heart rate
  - Respiratory rate
  - Temperature
  - Symptom assessment (CTCAE V4)
  - Assessment for concomitant medications
  - Assessment of compliance with study medication
  - Dose evaluation and escalation (where appropriate)
- Pharmacy
  - Dispense Axitinib (dose modification as per section 4.2 if applicable)

#### **5.2.6. Assessment at day 1, week 7 (within 7 days)**

- Laboratory determinations
  - FBC, coagulation, glucose, renal and liver function, serum calcium, CRP and LDH
  - Urinalysis
  - Serum thyroid function tests (Free T4 and TSH)
  - Blood and urine sample for biomarker analysis (NB. patients should be asked to fast for 6 hours prior to urine analysis)
- Clinical assessment
  - ECOG & Karnofsky performance status (appendix 1)
  - Body weight
  - Height
  - Blood pressure
  - Heart rate
  - Respiratory rate
  - Temperature
  - Symptom assessment (CTCAE V4)
  - Assessment for concomitant medications
  - Assessment of compliance with study medication
  - Dose evaluation and escalation (where appropriate)
- Pharmacy
  - Dispense axitinib (dose modification as per section 4.2 if applicable)

**5.2.7. Assessment at day 1, week 9 (within 7 days)**

- Laboratory determinations
  - FBC, coagulation, glucose, renal and liver function, serum calcium, CRP and LDH
  - Urinalysis
  - Blood and urine sample for biomarker analysis (NB. patients should be asked to fast for 6 hours prior to urine analysis)
- Clinical assessment
  - ECOG & Karnofsky performance status
  - Body weight
  - Height
  - Blood pressure
  - Heart rate
  - Respiratory rate
  - Temperature
  - Symptom assessment (CTCAE V4)
  - Assessment of compliance with study medication
- Radiological assessment
  - CT thorax, abdomen and pelvis (M1 patients) for IVC VTT and primary tumour assessment using RECIST 1.1 criteria and the Mayo classification
  - CT chest (M0 patients) for IVC VTT to check for development of chest metastasis.
  - Diffusion/ contrast enhanced MRI abdomen (all patients)

The patient should stop axitinib a minimum of 36 hours and a maximum 7 days prior to surgery; no further study drug should be dispensed.

**5.2.8. Surgery day 2-7, week 9 (+/- 7 days)**

- Surgery
  - Nephrectomy and IVC tumour thrombectomy

The surgeon should complete the surgery CRF on the day of surgery.

**5.2.9. Follow up assessment- 6 weeks post surgery (within 7 days)**

- Laboratory determinations
  - FBC, coagulation, glucose, renal and liver function, serum calcium, CRP and LDH
- Clinical assessment
  - ECOG & Karnofsky performance status (appendix 1)
  - Body weight
  - Height
  - Blood pressure
  - Heart rate

- Respiratory rate
- Temperature
- Symptom assessment (CTCAE V4)

#### **5.2.10. Follow up assessment- 12 weeks post surgery (within 7 days)**

- Laboratory determinations
  - FBC, coagulation, glucose, renal and liver function, serum calcium, CRP and LDH
  - Blood and urine sample for biomarker analysis (NB. patients should be asked to fast for 6 hours prior to urine analysis)
- Clinical assessment
  - ECOG & Karnofsky performance status (appendix 1)
  - Body weight
  - Height
  - Blood pressure
  - Heart rate
  - Respiratory rate
  - Temperature
  - Symptom assessment (CTCAE V4)
- Radiological assessment
  - CT thorax, abdomen and pelvis (all patients) for restaging.

#### **5.2.11. Imaging**

- All imaging data will be collated centrally.
- CT and RECIST assessment will be undertaken locally.
- MRI assessment will be undertaken at a single site to ensure consistency.

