## 3. TRIAL DESIGN

### 3.1. General Design

NAXIVA is a single arm, single agent, open label, phase II feasibility study of axitinib in patients with both metastatic and non-metastatic renal cell carcinoma of clear cell histology. 20 patients will be recruited from multiple centres within the United Kingdom.

Patients who have signed informed consent and who have met all eligibility criteria will be registered into the trial.

The starting dose of axitinib will be 5mg BID and escalated to 7mg BID and then 10mg BID. A dose modification assessment will take place every 2 weeks in clinic during the 8 week pre-surgical treatment period and will be dependent on tolerability of treatment. Patients will follow an aggressive axitinib dose escalation process within the 8 week period to a maximum of 10mg BID. Patients should stop axitinib a minimum of 36 hours and a maximum of 7 days prior to surgery in week 9.

Blood, urine and tissue samples will be taken prior to and during therapy to evaluate biomarkers of treatment response. Nephrectomy and IVC tumour thrombectomy will be planned for all patients on the trial.

Response to axitinib in VTT, primary tumour and any RECIST measureable lesion will be correlated with changes in molecular markers.

Patients will be followed up in clinic at 6 & 12 weeks post surgery.

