### **Primary Safety Endpoints**

Thirteen patients will be recruited at first; if at least 1 patient has an improvement in the Mayo classification a further 7 patients would be recruited (to the final total of 20 patients who have received study drug), to receive study drug. At least 3 patients showing reductions in Mayo score are required for a positive trial. The early stopping rules are:

- (1) If a single M0 patient progresses to the point where surgery is no longer possible, then recruitment of new patients will be suspended following a review by the data monitoring committee (DMC).
- (2) If a single M0 patient becomes M1 recruitment of new patients will be suspended following a review by the DMC.
- (3) If in 3 patients the VTT extends but patients remain surgically resectable the trial will close. If the VTT has extended the patient will be expedited and operated on as soon as possible.

Where there is diagnostic doubt at site, the week 3 MRI abdomen scans (and CT chest for M0 patients) a central review will be conducted to determine if a patient has progressed as per RECIST 1.1 criteria. In addition those particular patient cases will be discussed on an individual basis by the trial steering committee (TSC).

The central review for final analysis will be conducted by radiologists based at Addenbrooke's Hospital.

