## **9. STATISTICS**

### **9.1. Sample Size**

The aim is to recruit 20 patients over a 24 month period. A Simon two stage minimax design to distinguish a <5% from a >25% improvement in the Mayo classification requires 20 patients (90% power, 10% 1-sided). Thirteen patients would be recruited at first stage; if at least 1 patient had an improvement in the Mayo classification a further 7 patients would be recruited (to the final total of 20 patients).

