### **9.2. Analysis Plan**

The main analysis will be conducted on the “as-treated” population. All patients who receive study drug will be included in the interim and final analysis. Any patient who withdraws from the study prior to receiving drug will not be included in the analysis. At least 3 patients showing a reduction in Mayo Classification would produce a positive trial.

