1.2 Secondary endpoints

Secondary endpoints are:

- % change in surgical approach
- % change in VTT length
- Response rate (RECIST)
- Evaluation of surgical morbidity assessed by Clavian-Dindo classification

2 Study design

NAXIVA is a single arm, single agent, open label, phase II feasibility study of axitinib in patients with both metastatic and non-metastatic renal cell carcinoma of clear cell histology. 20 evaluable patients will be recruited from multiple centres within the United Kingdom.

Patients who have signed informed consent and who have met all eligibility criteria will be registered into the trial.

The starting dose of axitinib will be 5mg BID, escalated to 7mg BID and then 10mg BID. A dose modification assessment will take place every 2 weeks in clinic during the 8 week pre-surgical treatment period and will be dependent on tolerability of treatment. Patients will follow an aggressive axitinib dose escalation process

within the 8 week period to a maximum of 10mg BID. Patients should stop axitinib a minimum of 36 hours and a maximum of 7 days prior to surgery in week 9.

Blood, urine and tissue samples will be taken prior to and during therapy to evaluate biomarkers of treatment response. Nephrectomy and IVC tumour thrombectomy will be planned for all patients on the trial.

Where there is diagnostic doubt at site, a central review of week 0, 3 and 9 MRI and CT scans will be conducted to determine if a patient has progressed as per RECIST 1.1 criteria. In addition, those particular patient cases will be discussed on an individual basis by the trial steering committee (TSC). In addition, a central review of scans will be carried out once all scans have been carried out to ensure that all measurements are compliant with the NAXIVA MRI SOP (v2.1).

Patients will be assessed at weeks 1, 3, 5, 7, and 9 before surgery and followed up in clinic at 6 & 12 weeks post-surgery.

3 Reporting outline

This section outlines the planned content of interim, final analyses and, if relevant, additional statistical study reports.

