3.1.2 Early stopping rules

Stopping for reasons of futility: if zero evaluable patients have shown an improvement in disease, from screening to week 9, the trial will be stopped for futility. The rule for futility is specified in ([Section 1.1](#)) with further details set out in the efficiency analysis section ([Section 7.6.1](#)).

Stopping for reasons of patient safety: completion rates for patient safety data in the ITT population (see [Section 4.2](#) for population definition) to assess whether the early stopping rules have been violated will be prioritised for review by the DMC. Should data completion be adequate to assess the early stopping rules (i.e., complete data for thirteen patients), each rule will be assessed. If any rules are violated the trial will be stopped for reasons of patient safety. These rules are specified in [Section 5.2](#) with further details set out in the safety analysis section ([Sections 7.5.1, 7.5.2 and 7.5.3](#)).

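### Neither document says that the Mayo readers are masked to scan order, or names the read that decides the primary endpoint at the interim and final analyses

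*Protocol*

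**What the plan says.** Protocol 3.1 states that "NAXIVA is a single arm, single agent, open label, phase II feasibility study of axitinib". The primary endpoint is the percentage of evaluable patients whose Mayo level improves. SAP 1.1 and 7.6.1 add sub-location rules for patients who start at Level 0, and use the week 3 scan where there is no week 9 scan.

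The decision rule is in protocol 9.1 and 9.2. The design is meant to "distinguish a <5% from a >25% improvement in the Mayo classification requires 20 patients (90% power, 10% 1-sided". Stage one takes 13 patients, and seven more follow if any of the 13 improves. The rule for success at the end, in protocol 9.2, reads: "At least 3 patients showing a reduction in Mayo Classification would produce a positive trial". For the interim, SAP 3.1.2 has its own rule: "if zero evaluable patients have shown an improvement in disease, from screening to week 9, the trial will be stopped for futility".

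The reading arrangements are spread over several sections:

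- Protocol 5.2.11 bases the Mayo level on MRI and CT together. CT is assessed locally, while "MRI assessment will be undertaken at a single site to ensure consistency".
- Protocol 3.4 says: "The central review for final analysis will be conducted by radiologists" at a named hospital.
- SAP Section 2 says that "a central review of scans will be carried out once all scans have been carried out", and gives the purpose as compliance with the NAXIVA MRI SOP (v2.1).
- During the trial, central review applies only where a site is in diagnostic doubt, and the question is RECIST progression (protocol 3.4, SAP Section 2).

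Neither document mentions masking to date, time point or outcome for any Mayo read. Neither says which read prevails when reads differ, or which one feeds the futility decision.

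**The concern.** Every patient takes the drug, so a reader who knows the scan order knows which scan is on treatment. There is no control arm in which the same reading tendency could cancel out. The endpoint turns on anatomical boundaries: 2 cm from the ostium, the hepatic veins, the diaphragm and, at Level 0, renal vein branches or the gonadal vein. A small difference in judgement can move a patient across one of them. With only three improvements needed, a few such calls could decide the trial, and a positive result is meant to lead to a phase 3 trial (protocol 1.5).

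The interim raises a second question. The SAP's central review comes once all scans are done. If that review settles the Mayo level, the futility decision at 13 patients would have to use some other read of the same patients.

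**Working it through.** **Inputs.** First stage 13 patients, continue with at least 1 improvement; total 20, positive with at least 3; null rate 5%, target rate 25%, one-sided limit 10%, power 90% (protocol 9.1, 9.2). The rate d at which true non-improvers are read as improved is not in the documents. It is an assumption, shown as a range.

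**Step 1: reproduce the design.** With X ~ Bin(13, p) and Y ~ Bin(7, p),

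P(positive) = Σ over x ≥ 1 of P(X = x) · P(Y ≥ 3 − x).

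- p = 0.05: 0.3512 × 0.0444 (x = 1) + 0.1109 × 0.3017 (x = 2) + 0.0245 (x ≥ 3) = 0.0736.
- p = 0.25: 0.1029 × 0.5551 + 0.2059 × 0.8665 + 0.6674 = 0.9030.

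A full search also returns 13/20 as the minimax design. The plan's figures hold: type I error 7.4%, power 90.3%.

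**Step 2: false improvements in the deciding read at both analyses.** The observed rate becomes p = 0.05 + 0.95d, put through the same rule.

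| d (assumed) | Observed rate | P(positive) at true 5% |
|---|---|---|
| 0% | 5.00% | 7.4% |
| 1% | 5.95% | 11.0% |
| 2% | 6.90% | 15.2% |
| 3% | 7.85% | 20.0% |
| 5% | 9.75% | 30.3% |
| 10% | 14.50% | 56.2% |

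The same point in counts, at a true 5% rate and with the interim passed: one false improvement gives P(Bin(19, 0.05) ≥ 2) = 24.5%; two give P(Bin(18, 0.05) ≥ 1) = 60.3%.

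**Step 3: only the interim read is optimistic and the final read is sound.** A false read matters here only if none of the 13 truly improved and at least 3 of the next 7 do. The added risk is

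P(X = 0) · [1 − (1 − d)^13] · P(Y ≥ 3) = 0.5133 × [1 − (1 − d)^13] × 0.003757.

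- d = 5%: 0.5133 × 0.487 × 0.003757 = 0.0009, total 7.45%.
- Interim always passed: 0.5133 × 1 × 0.003757 = 0.0019, total 7.55%.

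**Step 4: what an optimistic interim read does cost.** Among 13 true non-improvers, the chance of at least one false improvement is 1 − (1 − d)^13: 23% at d = 2%, 49% at 5%, 75% at 10%. At a true 5% rate, the chance of stopping at 13 falls from 0.95^13 = 51.3% to 0.9025^13 = 26.4% at d = 5%. Each missed stop means up to 7 further patients treated.

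**Step 5: can the planned CT and MRI combination be masked?** By the protocol 5.1 schedule, CT covering the abdomen is done at screening in all patients, at week 3 in none, and at week 9 in M1 patients only. Abdominal MRI is done in all patients at all three times. The set of scans would therefore show the time point even with dates removed, except between screening and week 9 in M1 patients. MRI alone does not have this problem.

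**The case against.** Several stronger statements are tempting, and the documents do not support them.

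- *The scans are read unmasked.* The documents are silent, which is not the same thing. The MRI SOP v2.1 may set reading conditions. Even so, the SAP describes its Section 7 as the full operational specification of the analysis, and the reading rule for the primary endpoint is not there.
- *The end-of-trial central review is the deciding read.* Protocol 3.4 ties it to the final analysis, but the SAP gives its purpose as SOP compliance. Neither says that it overrides other reads. The gap is that no deciding read is named.
- *The interim must use different reads from the final analysis.* Single-site MRI assessment has no stated timing and may well exist at the interim; a later compliance review may change nothing. The text supports only that the reads may differ.
- *Optimistic interim reads could make the trial falsely positive.* There is no efficacy stop, and Step 3 shows almost no effect if the final read is sound.

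It can also fairly be said that the size rests on assumed rates with errors in one direction, and that masking would not remove ordinary reading error. If 20% of true improvers were also missed (equally an assumption), the 2% case gives 0.05 × 0.8 + 0.95 × 0.02 = 5.9% observed and 10.8% positive, not 15.2%. This stands, and it is why the figures show sensitivity and are not a forecast. Finally, this is a feasibility trial with a randomised trial to follow. That bears on how serious the point is; the remedy remains cheap.

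**Conclusion.** The point holds as a gap in the plan: masking to time point is not specified, and no read is named as deciding the primary endpoint at either analysis. The sample size and decision rule are correct as stated and need no change.

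The false-positive risk lies in the final deciding read. Under one-directional errors, a 1% false-improvement rate already takes the risk just past the 10% limit, and 5% takes it to 30.3%. Whether reading without masking would produce such rates cannot be settled from the documents. The interim problem is separate: it bears on exposing up to 7 more patients after a missed futility stop, and moves the false-positive risk from 7.4% to no more than about 7.55%.

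**What to change.** In protocol 5.2.11 and SAP Sections 2 and 7.6.1:

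1. Have the existing single-site central readers assign the Mayo level, and the Level 0 sub-location, from the abdominal MRI at screening, week 3 and week 9, with dates and identifiers removed and scans in random order.
2. Name this as the deciding read for the primary endpoint at both interim and final analyses, and say how disagreements between readers are resolved.
3. Complete it for the first 13 patients before the futility decision.
4. Amend the rule that combines MRI and CT, so that CT is a supporting or sensitivity read. Keep local reads for patient care and as a sensitivity analysis.

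If the MRI SOP already requires masked reading, state that in the SAP; items 2 to 4 would still be needed.

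The cost is the work of anonymising and shuffling images, an earlier reading session for the first 13 patients, and a primary read that relies on MRI where the protocol now uses MRI and CT together. Protocol 5.2.3 already asks for MRI coverage of the thrombus and the normal IVC beyond it. No extra scan is needed and 20 patients remain enough. This is a cheap improvement.
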